8. STUDY PROCEDURES

Only 1 study visit will be required.

The following procedures will be undertaken for the study, in time order:

1. Investigator to explain the study to patient, provide PIS, and obtain informed consent
2. CCT measurement using Occuity device
3. CCT measurement using Pentacam device
4. CCT measurement using Lenstar device
5. Instillation of Minims Proxymetacaine Hydrochloride 0.5% eye drops to the study eye
6. CCT measurement using Ultrasound Pachymeter

The devices will need cleaning between patients.

- The PM1 is to be cleaned with 70% isopropyl alcohol wipes to prevent patient-to-patient infection.
- The Lenstar device is to be cleaned with 70% isopropyl alcohol wipes will have the paper chin rest strip replaced.
- The Pentacam device is to be cleaned with 70% isopropyl alcohol wipes will have the paper chin rest strip replaced.
- The ultrasound probe will be wiped with a Q-tip soaked in 70% isopropyl alcohol. The tip will then be rinsed in sterile distilled water before use.

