2. SYNOPSIS

Study Title	Assessment of the Occuity PM1 pachymeter
Research question / hypothesis	Is the Occuity pachymeter non inferior in it's measurement of central corneal thickness compared to the ultrasound pachymeter, Lenstar and Pentacam.
Study Design	Research Study
Study Participants	Volunteers with no corneal pathology
Planned Sample Size	82-100 participants
Follow-up duration	N/A
Planned Study Period	1 month
Primary Objective	To determine whether the Occuity PM1 device is non-inferior in measuring central corneal thickness when compared to ultrasound pachymetry, the Lenstar and the Pentacam.
Secondary Objectives	The Investigation aims to assess long-term safety of the Occuity PM1 device when used under the conditions and for the purposes intended, to ensure it will not compromise the clinical condition or the safety of patients, or the safety and health of users or, where applicable, other persons.
Primary Endpoint	The central corneal thickness measurements taken by the three devices: Occuity PM1, the ultrasound pachymeter and Lenstar. Demonstrating that the Occuity PM1 Pachymeter is not inferior to the LenStar in terms of equivalency to a 95% confidence level using the Bland Altmen equation/approach based on +/-20micron equivalency.
Secondary Endpoints	If evidence is not sufficient to demonstrate that the PM1 Pachymeter does not perform outside of the target range, it is understood that further investigation may be required. If it is deemed that further clinical investigation(s) are required, it is understood that a new MHRA application will be undertaken.
Safety Outcomes	The type and number of adverse events, serious adverse events and any other device issues will be recorded. Adverse events and devices issues not reflected on the product label will be reported to the manufacturer and, for the Occuity product, will be dispositioned according to the Sponsor's complaint handling procedures for post-market products.
Intervention (s)	N/A

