7. SAMPLING

To achieve a statistically significant result in this crossover, non-inferiority study, with the alpha error set at <0.025, and power at 0.95, and a non-inferiority limit of 2 μ m, 163 eyes will be required, which would likely mean 82 to 100 participants, assuming most are able and willing to have tests performed on both eyes. Calculations are based on the formula:

$n = f(\alpha, \beta) \times 2 \times \sigma^2 / d^2$ (where σ is the standard deviation).

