15. INTERVENTIONS

15.1 Description of Study device

The Occuity PM1 device utilises both LED lights and low intensity infrared radiation. There are a total of 9 LED lights in a partial ring, the lights are at a radius of 8.75mm and spaced at 30° intervals. The total power is 2.4 mWm⁻² which is within the 10 mWm⁻² blue light hazard eye safety limit.

The infrared radiation is at a wavelength of 1310nm, and the maximum power is 50µW. The expected exposure to this radiation is less than 10 seconds in total, which makes it significantly under both the 2.5mW eye safe limit for 10 second exposure and the 158µW eye safe limit for 2-hour exposure, therefore the device is Class 1 eye safe according to BS EN 60825.

To take the measurement, the device will first be held above the study eye to achieve good alignment, after which the start button can be pressed to begin the measurement process. Once completed, the measurement will be displayed on the digital touchscreen of the device.

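### The sample size counts both eyes of most participants, but the procedures mention only an undefined study eye and never call for the second eye

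*Protocol*

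**What the plan says.** Protocol section 7 (Sampling) plans in eyes: "163 eyes will be required, which would likely mean 82 to 100 participants", with the proviso "assuming most are able and willing to have tests performed on both eyes". The synopsis carries only the participant count, "82-100 participants". The inputs given are "with the alpha error set at <0.025, and power at 0.95" and "a non-inferiority limit of 2 μ m". The formula is n = f(α, β) × 2 × σ² / d², but no value of σ is given (the text says only "where σ is the standard deviation").

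The operative steps are in section 8 (Study Procedures) and are repeated in section 12 (Study Assessments). The Occuity, Pentacam and Lenstar steps name no eye. The anaesthetic step before ultrasound reads "Instillation of Minims Proxymetacaine Hydrochloride 0.5% eye drops to the study eye". Section 15.1 says of the PM1 that "the device will first be held above the study eye to achieve good alignment".

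The term is not defined anywhere, no rule selects the eye, and section 7 is the only place that mentions both eyes.

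**The concern.** The planned size depends on second eyes, and nothing in the steps that staff will follow secures them. Section 3 says that patients need anaesthetic drops to tolerate the ultrasound probe. If drops go to one eye, only that eye can be measured by ultrasound. Section 3 calls ultrasound the gold standard, and section 17.2 lists PM1 against ultrasound as the first comparison.

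Because the optical steps name no eye, different clinicians could reasonably do different things: both eyes throughout, one eye throughout, or both eyes optically and one by ultrasound. Section 17.1 analyses participants who complete the study procedures, and on a literal reading one eye is enough for that. At stake are the number of eyes in the ultrasound comparison and the power stated for it. There is one visit, so readings not taken then can be recovered only by recalling volunteers.

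**Working it through.** **Inputs.** From section 7: 163 eyes, 82 to 100 participants, α 0.025 (sidedness not stated; taken as one-sided, as is usual for non-inferiority), power 0.95, limit d = 2 µm. From section 6.2: ±20 µm. Assumed: σ, the true difference between devices (zero), and independent eyes unless stated otherwise.

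**Reproducing 163.** f = (1.960 + 1.645)² = 12.995. Solving 163 = 12.995 × 2 × σ² / 2² gives σ = √(163 × 4 / (2 × 12.995)) = 5.01 µm. Conversely, σ = 5 gives 12.995 × 2 × 25 / 4 = 162.4, which rounds up to 163. So 163 is consistent with σ = 5, but cannot be derived from the stated inputs alone. (Taking 0.025 as two-sided would need σ = 4.65.)

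**Eyes to participants.** 163 / 2 = 81.5, rounded up to 82, which is the lower end of the range. To reach 163 eyes:
- with 82 participants, 163 − 82 = 81 must contribute both eyes (99%);
- with 100 participants, 163 − 100 = 63 must do so (63%).

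**One eye each.** This gives 82 to 100 eyes, or 50% to 61% of 163. The shortfall is 81 at 82 participants and 63 at 100. This step does not depend on σ.

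**Power at the 2 µm limit.** Power = Φ(2√n / (σ√2) − 1.96). For σ = 5 and n = 82: 2 × 9.055 / 7.071 = 2.561, less 1.96 = 0.601, and Φ = 0.726.

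| Eyes | σ = 4 | σ = 5 | σ = 6 |
|---|---|---|---|
| 82 | 89.3% | 72.6% | 56.9% |
| 100 | 94.2% | 80.7% | 65.4% |
| 163 | 99.5% | 95.1% | 85.3% |

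**Allowing for two eyes per person.** If the between-device differences in a person's two eyes have correlation ρ, 163 eyes in pairs carry the information of about 163 / (1 + ρ) independent eyes. At σ = 5:
- ρ = 0.5: 163 / 1.5 = 108.7, power 84%;
- ρ = 0.7: 163 / 1.7 = 95.9, power 79%.

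Both values of ρ are assumptions. They apply to the 82-participant end, where nearly everyone contributes both eyes. With 100 participants, 63 of them bilateral, ρ = 0.5 gives 63 × 2 / 1.5 + 37 = 121 and power 88%.

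**Power at ±20 µm, mean difference.** With 82 eyes, 20 × 9.055 / 7.071 = 25.6 standard errors at σ = 5, and 20 × 9.055 / 8.485 = 21.3 at σ = 6. Power is essentially 100% either way.

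**The case against.** The strongest reply is that no one-eye rule exists. Nothing in the protocol says one eye per participant, selects an eye or excludes the fellow eye. Section 12 repeats section 8, and section 15.1 only describes how a single reading is taken, which is necessarily on one eye at a time. Section 7 expects both eyes to be tested. If *study eye* means each eye under study, the sections agree. This largely stands. It removes any claim that the design is one eye per participant, but the term remains undefined and no step asks for the second eye.

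Three stronger readings are tempting, and the document does not support them:

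- **That the whole study would have 82 to 100 eyes.** The phrase appears in the procedure lists only at the anaesthetic step. The optical steps, including PM1 against Lenstar, the comparison with the stated success criterion, are not limited by it.
- **That the paired design breaks.** Section 17.2 sets PM1 against ultrasound separately from the optical comparisons. A fellow eye without ultrasound drops out of the former and leaves the latter intact.
- **That power should be judged for two-sided equivalence at ±2 µm.** The protocol states no such test: section 7 has a 2 µm non-inferiority limit and section 6.2 has ±20 µm equivalency.

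The contrast of 73–81% with 95% also flatters the two-eye plan, because 95% treats all 163 eyes as independent. Against 84% (ρ = 0.5, 82 participants), the loss from measuring one eye is smaller.

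Finally, section 6.2 uses ±20 µm, where power for the mean difference is near 100% in any case. That stands for the mean. If the criterion were instead that the 95% confidence limits of the Bland-Altman limits of agreement lie within ±20 µm, the result would depend on σ: by simulation with zero bias and independent eyes, 82 eyes give about 98% at σ = 5 and about 38% at σ = 6.

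**Conclusion.** The point holds as an unreconciled inconsistency between the sample size and the procedures. It is not evidence that one eye was intended. Read literally, the ultrasound comparison has 82 to 100 eyes, 63 to 81 short of 163, and that shortfall needs no assumption about σ. Even if both eyes were intended, the plan needs 63% to 99% of participants to contribute both, and no procedural step provides for it.

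The power loss at 2 µm, to 73–81% from the stated 95%, rests on a back-solved σ of 5 µm, zero true difference, a one-sided 0.025 level and independent eyes. Over σ of 4 to 6 the one-eye power runs from 57% to 94%. At ±20 µm the mean-difference comparison is hardly affected. The gap between 2 µm and ±20 µm is a separate matter.

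**What to change.** Reconcile sections 7, 8 and 12 by stating whether one or both eyes are measured on all four devices, and define *study eye* accordingly.

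- **If both:** say so in each measurement step and at the anaesthetic step, and say what happens when only one eye is available. Analyse with the participant as the cluster, and restate the power with a stated σ and between-eye correlation (for example about 84% at σ = 5 and correlation 0.5 with 82 participants).
- **If one:** say how the eye is chosen, and restate the planned size as 82 to 100 eyes with the power that this gives. Keeping 163 eyes would need 163 participants.

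The cost is a few words in the procedures and a revised sampling paragraph, with a stated power below 95% at the 2 µm limit if σ is about 5. It should be settled before the first visit.

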9. RECRUITMENT

Recruitment will be volunteers of Occuity who will be independently assessed and monitored by qualified clinicians from City, University of London.

10. SCREENING AND ENROLMENT

Eligible participants will be approached during their visit and will be given verbal information as well as the patient information sheet (PIS). Adequate time will be given for eligible patients

to read the PIS and make decision about participation in the study. Informed consent will be obtained by qualified study staff who have had Good Clinical Practice (GCP) training before undertaking any study specific procedures.

A copy of the signed Informed Consent Form (ICF) will be given to the patient. The original signed ICF will be kept in the site study folder and a copy of the signed ICF will be filed in the patient's notes. Consenting procedure will be clearly documented in patient's notes with date and signature.

11. RANDOMISATION

The volunteers will be randomised *a priori* into one of two sequences – those in Sequence 1 who follow the sequence Lenstar, Pentacam, PM1 then ultrasound and Sequence 2 who will follow the sequence Pentacam, PM1, Lenstar, ultrasound. The order in which subjects will be allocated to each sequence will be generated by a validated software prior to the start of the study to allocate the volunteers to each sequence.

NOTE: Ultrasound cannot be included within the randomisation as the anaesthesia required to undertake the US methodology would result in the Occuity PM1 & Lenstar measurements being unable to be recorded.

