5. STUDY DESIGN

6.1 Summary of Study Design

This is a prospective, observational, non-invasive, crossover study. The participants will undergo CCT measurement using the Occuity PM1 device, Lenstar device, the Pentacam and then the Ultrasound pachymeter, which is standard of care. Measurement with ultrasound will occur last, as this will require instillation of anaesthetic drops which may confound the values obtained by the Occuity and other devices.

The participants will be recruited and will be measured by City University Clinicians. No additional visits will be required. The measurements will take place during their clinic appointment and will take approximately 30 minutes to complete.

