6.2 Primary and Secondary Endpoints/Outcome Measures

The central corneal thickness measurements taken by the three devices: Occuity PM1, the ultrasound pachymeter and Lenstar. Demonstrating that the Occuity PM1 Pachymeter is not inferior to the LenStar in terms of equivalency to a 95% confidence level using the Bland Altmen equation/approach based on +/-20micron equivalency.

Occuity outlines the target range of the PM1 to be within 300-800um. This is because we have already tested this target range with known artefacts. However, the patient population which

is being evaluated will consist only of patients with no known corneal abnormalities, corrective refractive surgeries, ocular inflammatory conditions etc.

It is likely that ~95% of corneal thicknesses which are measured will be within the range of 480um to 620um, therefore ~5% will be outside of the expected range. However, despite there being no history of the pre-stated conditions, there is still the likelihood of this study being able to assess patients with thick/thin corneas as part of the scope, as this is the percentage population who naturally have very thin or very thick corneas.

Secondary Endpoint

If evidence is not sufficient to demonstrate that the PM1 Pachymeter does not perform outside of the target range, it is understood that further investigation may be required. If it is deemed that further clinical investigation(s) are required, it is understood that a new MHRA application will be undertaken.

SAFETY OUTCOMES MEASURES

The type and number of adverse events, serious adverse events and any other device issues will be recorded. Adverse events and devices issues not reflected on the product label will be reported to the manufacturer and, for the Occuity product, will be dispositioned according to the Sponsor's complaint handling procedures for post-market products.

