12. STUDY ASSESSMENTS

After informed consent is obtained, a short targeted medical and ocular history will be taken, which focuses on whether there is any known corneal pathology, or other ocular or systemic condition which would affect the study assessments needed.

Then the following assessments will take place:

1. CCT measurement using Occuity device
2. CCT measurement using Pentacam device
3. CCT measurement using Lenstar device
4. Instillation of Minims Proxymetacaine Hydrochloride 0.5% eye drops to the study eye
5. CCT measurement using Ultrasound Pachymeter

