17.2 Analysis of Endpoints

On completion of data collection, the primary endpoint will be analysed using paired tests or non-parametric equivalents, to compare the CCT measurement achieved using the ultrasound pachymeter and the Occuity PM1 device, and then between the values obtained from the Lenstar, Pentacam and Occuity PM1 device. The level of statistical significance will be set at $p < 0.05$.

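### Sections 8 and 12 put PM1 first for everyone, while Section 11 randomises to two sequences in which PM1 is never first, so no participant can follow both

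*Protocol*

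**What the plan says.** All locations are in the protocol.

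- **Section 11 (Randomisation)** allocates each volunteer to one of two orders: "Sequence 1 who follow the sequence Lenstar, Pentacam, PM1 then ultrasound and Sequence 2 who will follow the sequence Pentacam, PM1, Lenstar, ultrasound". It adds that "The order in which subjects will be allocated to each sequence will be generated by a validated software" before the study starts.
- **Section 8 (Study Procedures)** opens its list with "The following procedures will be undertaken for the study, in time order". The measurements are then PM1, Pentacam, Lenstar, anaesthetic drops, ultrasound. No sequence or allocation is mentioned.
- **Section 12 (Study Assessments)** introduces a numbered list with "Then the following assessments will take place" and gives the same order, again for all participants.
- **Section 6.1 (Summary of Study Design)** names the devices in a further order: PM1, Lenstar, Pentacam, then ultrasound. It also states the design: "This is a prospective, observational, non-invasive, crossover study". Section 7 (Sampling) repeats the label: "To achieve a statistically significant result in this crossover, non-inferiority study".
- **Section 17.2 (Analysis of Endpoints)** says "the primary endpoint will be analysed using paired tests or non-parametric equivalents".
- **Section 6.2** sets the only stated acceptance criterion, for PM1 against Lenstar, "using the Bland Altmen equation/approach based on +/-20micron equivalency".

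The four descriptions of the order agree on one thing only: ultrasound comes last.

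**The concern.** The protocol gives two incompatible instructions for taking the primary measurement, and following either is a deviation from the other. Sections 8 and 12 are the ones a site would work from at the visit, and nothing in them points to Section 11. No section says which takes precedence.

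What is at stake is the purpose of the randomisation. A single fixed order is not a crossover. If every participant is measured in the Section 8 order, any effect of being measured first, second or third is inseparable from the difference between devices. If practice is mixed, the comparison can be recovered only if the order actually used is known for each participant.

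A lesser point concerns Section 11 itself. Pentacam immediately precedes PM1 in both sequences, so that pair never changes places, although Pentacam is a named comparator in the primary objective.

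**Working it through.** **1. Positions side by side** (ultrasound is fourth throughout)

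| Source | PM1 | Pentacam | Lenstar |
|---|---|---|---|
| Sections 8 and 12 | 1 | 2 | 3 |
| Section 11, Sequence 1 | 3 | 2 | 1 |
| Section 11, Sequence 2 | 2 | 1 | 3 |
| Section 6.1, as listed | 1 | 3 | 2 |

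Neither randomised sequence equals the fixed order.

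**2. What can be estimated.** Let p1, p2, p3 be additive position effects, a = p2 − p1 and b = p3 − p1. Let dL and dP be the true PM1 − Lenstar and PM1 − Pentacam differences. The expected mean paired differences are:

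- Sequence 1: A1 = dL + b; B1 = dP + b − a
- Sequence 2: A2 = dL + a − b; B2 = dP + a
- Section 8/12 order: A3 = dL − b; B3 = dP − a

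Section 11 gives four equations in four unknowns. A1 − A2 = 2b − a and B1 − B2 = b − 2a, so b = [2(A1 − A2) − (B1 − B2)]/3 and

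dL = A1 − b = (A1 + B1)/3 + (2·A2 − B2)/3.

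The Section 8/12 order alone gives two equations in four unknowns, so dL and dP are not estimable.

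**3. Price of adjusting for position under Section 11.** Assume one reading per device, independent errors with variance σ², and 84 participants split 42/42 (no allocation ratio is stated). Each mean difference within a sequence has variance 2σ²/42, and A and B in the same sequence have covariance σ²/42.

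- Sequence 1 part: (2 + 2 + 2)/9 = 6/9
- Sequence 2 part: (4×2 + 2 − 4)/9 = 6/9
- Var(dL) = (12/9) × σ²/42
- Unadjusted paired mean: 2σ²/84 = σ²/42
- Ratio = 12/9 = 1.333; standard error × √1.333 = 1.155

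The ratio for dP is the same.

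**4. Mixed practice.** Least squares with participant effects and categorical position, 84 participants, variance relative to the unadjusted paired comparison:

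| Sequence 1 / Sequence 2 / Section 8 order | Variance ratio |
|---|---|
| 42 / 42 / 0 | 1.333 |
| 38 / 38 / 8 | 1.217 |
| 21 / 21 / 42 | 1.371 |
| 4 / 4 / 76 | 5.516 |
| 0 / 0 / 84 | not estimable |

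The ratios depend on the proportions in each order, not on the total of 84. They require the order used to be known.

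**5. Bias of an unadjusted paired comparison.** From step 2, averaging the two sequences 1:1:

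- Section 11: PM1 − Lenstar (p2 − p1)/2; PM1 − Pentacam (p3 − p1)/2
- Section 8/12: PM1 − Lenstar p1 − p3; PM1 − Pentacam p1 − p2

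The protocol gives no order-effect size, so this is illustration only. For a linear drift of 0.5, 1 or 2 µm per position:

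| Order | PM1 − Lenstar (µm) | PM1 − Pentacam (µm) |
|---|---|---|
| Section 11 | 0.25, 0.5, 1.0 | 0.5, 1.0, 2.0 |
| Section 8/12 | −1, −2, −4 | −0.5, −1, −2 |

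Against 20 µm, the PM1 − Lenstar bias is 1.25% to 5% under Section 11 and 5% to 20% under Sections 8/12. Other shapes change size and sign: with p = (0, 0, 1), the PM1 − Lenstar bias is 0 under Section 11 and −1 under Sections 8/12.

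**The case against.** The strongest reply is that the harm depends on a position effect for which the protocol offers no evidence. Its only stated order concern is the anaesthetic, and every section puts ultrasound last. Even with drift as assumed above, the PM1 − Lenstar bias stays well inside ±20 µm. Section 11 is the only section on allocation and calls for a list made in advance, so a sensible site would probably follow it. Some mixing does little harm if the order is known: 8 of 84 measured off-sequence gives 1.22, slightly better than full compliance at 1.33.

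Most of this is fair as to size, and it means the damaging case is near-universal use of the Section 8 order. It does not remove the contradiction. The protocol does not say that Section 11 governs, and the sponsor evidently thought order worth randomising. Against the 2 µm limit used for the sample size, the same drift would not be small.

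Three narrower points stand:

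- Only Section 8 says its list is chronological. Section 12 implies it by numbering, so the contradiction rests on Section 8 with Section 12 in support.
- Separation under Section 11 assumes additive position effects and no carryover. With four means and four unknowns, that assumption cannot be checked from those means.
- The balance of the two sequences is a secondary matter. The analysis plan, which is not at hand, may include a position term, so its absence is not claimed as a defect.

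**Conclusion.** The contradiction holds on the text alone and needs no numerical assumption: PM1 is first for everyone under Sections 8 and 12 and for nobody under Section 11. It must be corrected before enrolment, because following Section 8 throughout would turn a randomised crossover into a fixed-order study in which device and position cannot be separated.

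The size of any resulting bias is unknown. The micrometre figures rest on an assumed linear drift. The variance ratios rest on additive position effects, no carryover, one reading per device, independent errors and, for Section 11, equal allocation. No carryover between the optical devices is claimed. The imbalance within Section 11 is minor against the ±20 µm PM1 − Lenstar criterion.

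**What to change.** **Required.** State that the randomised sequence governs. Reword Sections 6.1, 8 and 12 so that the optical devices are used in the participant's allocated sequence, with ultrasound last. Record on the case report form the order actually used, if the form does not already capture it. The cost is a few lines of text and at most one data field.

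**Optional.** Either of these deals with the remaining imbalance in Section 11:

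- Include measurement position in the analysis. The existing two sequences allow it at 1.33 times the variance of the unadjusted paired comparison.
- Balance the list so that position cancels at 1.00 times. Adding PM1–Lenstar–Pentacam–ultrasound completes a three-row Latin square; 84, 87, 90, 93, 96 or 99 participants fit the planned 82 to 100. All six orders of the optical devices would also do, with 84, 90 or 96.

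Balancing the list uses the same devices, visit, measurements and sample-size range. Its price is slightly more complicated site logistics and more scope for wrong-order errors.

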4. AIMS AND OBJECTIVES

Primary Objective

To determine whether the Occuity PM1 device is non-inferior in measuring central corneal thickness when compared to ultrasound pachymetry, the Lenstar and the Pentacam.

Secondary Objective

The Investigation aims to assess long-term safety of the Occuity PM1 device when used under the conditions and for the purposes intended, to ensure it will not compromise the clinical condition or the safety of patients, or the safety and health of users or, where applicable, other persons.

If the evidence collected during this investigation is not sufficient to demonstrate that the PM1 Pachymeter does not perform under the conditions and for the purposes intended, it may be deemed possible that further investigation may be required. If it is deemed that further clinical investigation(s) are required, it is understood that a new MHRA application will be undertaken.

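### With the two sequences in Section 11, PM1 is never first and always directly follows Pentacam, so Pentacam carry-over cannot be separated from PM1 and plain paired tests keep a period effect

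*Protocol*

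**What the plan says.** Section 6.1 gives the design: "This is a prospective, observational, non-invasive, crossover study". Section 11 randomises volunteers "into one of two sequences": "Sequence 1 who follow the sequence Lenstar, Pentacam, PM1 then ultrasound and Sequence 2 who will follow the sequence Pentacam, PM1, Lenstar, ultrasound". It states no allocation ratio. It sets ultrasound apart on purpose ("Ultrasound cannot be included within the randomisation"), because of the anaesthetic.

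The primary objective in Section 4 is non-inferiority of PM1 "when compared to ultrasound pachymetry, the Lenstar and the Pentacam". The success statement in Section 6.2 concerns PM1 against Lenstar, "using the Bland Altmen equation/approach based on +/-20micron equivalency". Pentacam is not among the three devices listed in that endpoint and has no success criterion there. Section 7 sizes the study on a 2 µm limit.

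Section 17.2 says that "the primary endpoint will be analysed using paired tests or non-parametric equivalents". It mentions no period or sequence term.

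Section 8 introduces its own list with "The following procedures will be undertaken for the study, in time order" and gives PM1, Pentacam, Lenstar, ultrasound for everyone. Section 12 repeats that order. It is neither of the two sequences in Section 11.

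**The concern.** Order is randomised in a crossover so that the effect of being measured earlier or later, or just after a particular device, is not read as a difference between devices. For that to work in a simple paired comparison, each device should occupy each position equally often. To protect against carry-over as well, each device should follow each other device equally often.

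The two sequences in Section 11 do neither. PM1 takes positions 3 and 2, Pentacam 2 and 1, and Lenstar 1 and 3. PM1 has the same immediate predecessor in all participants. The PM1-Lenstar order is reversed between sequences, but unevenly: two places later in one, one place earlier in the other.

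Two comparisons named in the primary objective are at stake. The order of measurement is fixed at the visit, so a missing order cannot be supplied afterwards by analysis.

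**Working it through.** **The plan's own figures.** The protocol gives no figure for drift or carry-over, so none can be reproduced. The 2 µm limit used below as a scale comes from Section 7, which asks for 163 eyes by n = f × 2σ²/d², with alpha 0.025, power 0.95 and d = 2 µm. With f = (1.960 + 1.645)² = 12.995 and an assumed σ of 5 µm (no value is stated), n = 12.995 × 2 × 25/4 = 162.4, rounded up to 163. Nothing below depends on this figure.

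**Inputs.** The sequences are from Section 11 and the paired analysis from Section 17.2. Assumptions: 1:1 allocation, and a drift δ of 0.5-1 µm per position. Notation: M = PM1, P = Pentacam, L = Lenstar; π1, π2, π3 are the position effects; λ with a device subscript is what that device leaves behind in the next reading.

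| | Sequence 1 | Sequence 2 | Mean at 1:1 | If drift is linear |
|---|---|---|---|---|
| M−P, position gap | 3−2 = +1 | 2−1 = +1 | +1 | |
| M−P, period bias | π3−π2 | π2−π1 | (π3−π1)/2 | 1.0δ |
| M−L, position gap | 3−1 = +2 | 2−3 = −1 | +0.5 | |
| M−L, period bias | π3−π1 | π2−π3 | (π2−π1)/2 | 0.5δ |

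For linear drift, the M−P bias is δ at any allocation ratio. If a share p is in Sequence 1, the M−L bias is (3p−1)δ: 0.5δ at p = 0.5, 0.8δ at 0.6 and zero at one third.

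**Size.**
- M−P: 0.5-1.0 µm, which is 25-50% of 2 µm and 2.5-5% of 20 µm.
- M−L: 0.25-0.5 µm, which is 12.5-25% of 2 µm and 1.25-2.5% of 20 µm.

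**Can a model remove the period effect?** Let a = π2−π1 and b = π3−π2. The successive within-person differences are:
- Sequence 1: A = P−L+a and B = M−P+b.
- Sequence 2: C = M−P+a and D = L−M+b.

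Then C−A = M+L−2P and D−B = L+P−2M, so M−P = [(C−A)−(D−B)]/3. Likewise M−L = −[(C−A)+2(D−B)]/3. Both are free of a and b.

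The cost is variance. With one person per sequence and unit within-person variance, the plain estimate (B+C)/2 has variance (2+2)/4 = 1.00. The adjusted one is [(B−A)+(C−D)]/3, with variance (6+6)/9 = 1.33.

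**And carry-over?** In the plain paired means, carry-over adds λP−λL/2 to M−P and λP−λM/2 to M−L. In the period-adjusted M−P it adds λP−(2λL+λM)/3. A carry-over equal for all three devices cancels there, because it acts like a period effect; a Pentacam-specific one stays in full. The six sequence-by-position means are already fitted by six parameters (two sequence, two period, two device), so nothing is left to test for carry-over. A rank check confirms that once first-order carry-over terms are added, neither contrast is estimable.

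**Alternative designs (optical devices only).**
- Adding PM1, Lenstar, Pentacam as a third sequence completes the 3×3 Latin square. Position effects of any shape cancel at 1:1:1. Among these three orders, PM1 is still preceded only by Pentacam when it is not first. Carry-over becomes estimable, but the variance of either contrast rises from 0.67 to 3.33, a factor of 5.
- All six orders balance both position and predecessor. The plain M−P mean keeps only (λP−λM)/3, and modelling carry-over raises the variance from 0.333 to 0.417, a factor of 1.25.

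**The case against.** The strongest reply has four parts.

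1. The two sequences are two rows of a Latin square, so a model with period terms recovers both optical contrasts. The statistical analysis plan is not shown and may contain such a model. This stands. A reader might infer that PM1-Pentacam is wholly confounded with position and that no analysis of these sequences can help. That is wrong for period effects, as the algebra shows; it is right only for carry-over.

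2. Nothing in the protocol points to carry-over between the optical devices. Sections 3 and 15.1 describe PM1 as an optical device exposing the eye to low power for under ten seconds. Section 3 says Lenstar and Pentacam need neither drops nor corneal touch. The only confounder named is the anaesthetic, and ultrasound is placed last for that reason. This stands too. The documents do not show that carry-over exists, only that the design could not detect or remove it if it did.

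3. Lenstar, the comparator in the success statement, does have its order reversed relative to PM1, so a linear drift is halved without any adjustment. This is correct, and a claim that the PM1-Lenstar result would be invalid is not supported.

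4. The drift is assumed, and against 20 µm the bias is minor. This also stands. It could matter only on the 2 µm scale, and the protocol uses both scales.

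What survives is the order that is never reversed, the carry-over that cannot be separated, and the period effect left by the analysis as Section 17.2 states it.

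**Conclusion.** The point holds as a cheap design improvement, not as a flaw that undermines the trial. PM1 is never first and always directly follows Pentacam, so carry-over specific to Pentacam cannot be separated from the PM1 effect. Paired tests without a period term leave the period effect in PM1-Pentacam and half a position step of a linear drift in PM1-Lenstar. A period-adjusted model would remove the drift but not the carry-over.

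The size rests on two assumptions, a drift of 0.5-1 µm per position and 1:1 allocation. The true drift may be zero.

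The conclusion also takes Section 11 as governing. If the single order in Sections 8 and 12 were followed, no order would be reversed at all and a linear drift would bias PM1-Pentacam by −1δ and PM1-Lenstar by −2δ. The PM1-ultrasound comparison is outside this point: ultrasound is deliberately last, and its position stays confounded under any of these designs.

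**What to change.** In Section 11, randomise equally across all six orders of the three optical devices, each followed by ultrasound, and state the allocation ratio. This balances position and immediate predecessor.

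At minimum, add a third sequence (PM1, Lenstar, Pentacam, ultrasound) at 1:1:1. This cancels any period pattern but does not balance carry-over. Simply adding the reverse of each existing sequence is less good: it cancels linear drift only and leaves (2π2−π1−π3)/4 in PM1-Lenstar.

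Reconcile Sections 8 and 12 with Section 11, so that the procedure lists refer to the allocated sequence and not to one fixed order.

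Cost: an amended paragraph in Section 11, matching edits in Sections 8 and 12, and an allocation list regenerated before the first participant. No participants, visits or procedures are added. The downside is that staff must follow six orders (or three) instead of two, so the allocated order should be on the case report form.
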